3.3. Contraindication Cohort

Up to 150 additional subjects who meet study eligibility criteria and who have an absolute contraindication to thrombolytics, whose initial planned primary treatment strategy includes FlowTriever, will be evaluated as part of the Contraindication Cohort. The same RCT Cohort clinical assessments and follow up schedule will be administered in the Contraindication Cohort.

4. Incomplete Date Handling and Missing Data

Partial date/time input will not be collected in the electronic case report form (eCRF), i.e., date/time will be either non-missing or completely missing. On a case-by-case basis, when the missing date/time imputation is required, the most conservative date/time will be used.

In general, main analysis will be conducted in the complete case analysis. Additional sensitivity analysis will be conducted by imputing missing data using multiple imputation.

PROPRIETARY AND CONFIDENTIAL

The information contained in this document is the sole property of Inari Medical

	PEERLESS Study: Statistical Analysis Plan	Version 5.0 March 22, 2024 Page 15 of 25
---	--	--

5. Statistical Methods and Analysis

5.1. Sample Size

By assuming an 80% power with one-sided alpha of 2.5%, the win ratio methodology is applied to the primary endpoint that consists of five components. The required sample size is 432 subjects (216 subjects per arm); and planning for follow up attrition and further describing secondary endpoints/exploratory analysis, the study will enroll up to a total of 550 randomized subjects (RCT Cohort). The "event" proportions of the five components are based on Inari sponsored studies and a review of literature.

Up to 150 additional subjects who meet all eligibility criteria and who have an absolute contraindication to thrombolytics, whose initial planned primary treatment strategy includes FlowTriever, will be enrolled as part of the Contraindication Cohort. The same clinical assessments and follow up schedule will be administered in this cohort as is described for the RCT Cohort.

5.2. Statistical Methodology

[figure not shown]
The statistical design objective for this trial is to compare the clinical outcomes of the FlowTriever System versus CDT for use in the treatment of acute pulmonary embolism (PE). Since the primary endpoint is a composite clinical endpoint, a modified generalized Wilcoxon test (F-S test) proposed by Finkelstein & Schoenfeld⁴ will be applied to examine the performance differences between the two treatment arms.

In this trial, the primary endpoint is a hierarchy of five clinical outcome components. Each subject in the study will be compared to each of the other subjects in a pairwise manner, regardless of which treatment arm the compared subject is in, and assigned a score, u_{ij} , of 1, -1, or 0, depending on whether the comparison has a favorable, unfavorable, or unsettled outcome in the hierarchy of the clinical events; i is the index subject to be compared with all other subjects in a pairwise fashion and j represents j^{th} subject comparison. For example, if a subject i is alive while a subject j died, the score is 1; if a subject i died while subject j is alive, the score is -1. If both subjects are alive/dead or any subject is missing in mortality status (i.e., a pair is unsettled/not comparable for the first outcome), the second clinical outcome (Intracranial hemorrhage) is compared and assigned a score of 1, -1, or unsettled in a similar comparison logic. Subsequently, within each pairwise comparison, the score is determined by comparing five clinical outcomes sequentially in the order of outcome priorities (see Figure 2). In summary, for each pair of subjects (i, j) , the score is defined as

$$u_{ij} = \begin{cases} 1, & \text{if subject } i \text{ does better than subject } j \\ -1, & \text{if subject } j \text{ does better than subject } i \\ 0, & \text{if it cannot be determined} \end{cases}$$

PROPRIETARY AND CONFIDENTIAL

The information contained in this document is the sole property of Inari Medical

Figure 2 Pairwise Comparison Flowchart

Finkelstein & Schoenfeld⁴ (F-S) then assigned a score $U_i = \sum_{i \neq j} u_{ij}$ to each subject i . Their proposed test is a score test based on the sum of the ranks for the treated group (see the following equation).

$$T = \sum_{i=1}^N U_i D_i$$

where $D_i = 1$ for subjects in FlowTriever arm and $D_i = 0$ for subjects in CDT arm, and N is the number of total subjects in the trial. The proposed F-S statistic for the hypothesis of interest is T / \sqrt{V} , where $V = \frac{n_{FT} n_{CDT}}{N(N-1)} \sum_i U_i^2$ is the variance of T , n_{FT} and n_{CDT} are the number of subjects in FlowTriever and CDT

PROPRIETARY AND CONFIDENTIAL

The information contained in this document is the sole property of Inari Medical

	PEERLESS Study: Statistical Analysis Plan	Version 5.0 March 22, 2024 Page 17 of 25
---	--	--

arms, respectively, and $n_{FT} + n_{CDT} = N$. The hypothesis is tested by comparing the F-S statistic to the standard normal distribution (Finkelstein & Schoenfeld⁴).

To determine the sample size required to achieve 80% power given one-sided alpha of 2.5%, we first will simulate subject level data per data replicate. For a data replicate and within a treatment arm, clinical outcomes with event proportions are sampled from binomial distribution; ICU is from a multinomial distribution with 3 categories, including no ICU admission, ≤ 24 hours, and > 24 hours. We will assume each of the clinical outcomes are independent of each other. For example, we may sample 100 subjects per treatment arm, and within each treatment arm each has different clinical outcome proportions or means. Once we generate 200 subjects in total (100 per treatment arm), we may derive the F-S test statistic and its p-value. We will then repeat the process for 2,500 data replicates and derive 2,500 p-values based on F-S test statistics; power is the proportion of p-values that are ≤ 0.05 . Each given sample size number will thus lead to one power number to be calculated. As we alter the sample sizes in the simulation scenario, we can conduct a grid search to determine the minimal sample size required to achieve at least 80% power.

The primary and secondary endpoints will be analyzed for both ITT and PP populations, separately. Primary endpoint and secondary endpoints will lead to hypothesis testing whereas, only descriptive summary statistics will be provided for the Contraindication Cohort.

5.3. Primary Endpoint Analysis

The primary endpoint for this study will be assessed using the F-S statistic with the following null and alternative hypotheses:

$$H_0: n_{FW} \leq n_{CW} \text{ versus } H_A: n_{FW} > n_{CW}$$

where n_{FW} is the random variable of the number of winners for the FlowTriever System (i.e., counting the number of pairs in which the subject i in FlowTriever System does better than those in CDT arms) while n_{CW} is the random variable of the number of winners for the CDT (i.e., counting the number of pairs in which the subject i in FlowTriever System does worse than those in CDT arms).

To separately quantify the treatment effect of interest, the win ratio of the treatment effect is defined by Pocock et al.⁵, where the performance differences between the two treatment arms is defined as $\frac{N_{FW}}{N_{CW}}$, where N_{FW} is the number of winners for the FlowTriever System and N_{CW} is the number of winners for CDT in the dataset; the 95% CI of the win ratio estimate can be derived via a bootstrap method, a method whereby the original data is sampled with replacement with a large number of times, e.g. 1000 samples being drawn to create 1000 datasets. From each bootstrap sample, the win ratio of the treatment effect is computed and an empirical distribution of the win ratio is determined from the total number of sample datasets. The lower and upper limits of the 95% CI are the 2.5%ile and 97.5%ile

PROPRIETARY AND CONFIDENTIAL

The information contained in this document is the sole property of Inari Medical

	PEERLESS Study: Statistical Analysis Plan	Version 5.0 March 22, 2024 Page 18 of 25
---	--	--

of this empirical distribution of the win ratio out of 1000 samples. In this study, FT and CDT groups are labelled **F** and **C** with n_F and n_C subjects, respectively. The following are the five steps of calculating 95% CI via a bootstrap approach:

1. Draw a random sample S_F of size N_F (275) with replacement from the original FT group and a random sample S_C of N_C with replacement from original CDT group. In this study, $S_F = S_C$.
2. Perform the unmatched analysis, all possible pairs comparison, on the samples S_F , S_C and calculate the win ratio of the treatment effect.
3. Repeat Steps 1 and 2 1000 times.
4. Determine the empirical bootstrap distribution of the win ratio from the 1000 bootstrap values.
5. Obtain the 2.5%ile and 97.5%ile of the bootstrap distribution which are the estimated limits of the 95% confidence interval of the win ratio.

The hypothesis testing using the F-S statistic and the estimation of the win ratio of the treatment effect of the primary endpoint will be assessed in both ITT and PP populations. If the results of the ITT and PP populations are similar, it indicates robust confidence on the treatment effect of FT relative to CDT.

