3.1. Intention To Treat Population

All subjects who met the inclusion/exclusion criteria, provided informed consent, and who were randomized to the FlowTriever or CDT group will be included in ITT. To be included in ITT, subjects must receive some treatment for PE after randomization. This study will consist of up to 550 subjects with acute PE who meet the eligibility criteria, and are enrolled, consented, and randomized. Subjects will be excluded from ITT population if no treatments were given, or no data were available after randomization.

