3.2. Per Protocol Population

Per Protocol (PP) population is a subset of ITT population that adhere to the protocol. The following are some of the possible reasons to exclude subjects from PP population.

- Non-compliant
- Protocol deviations
- Withdrawn from study
- Received other PE treatments than the assigned

The primary and secondary endpoints will be analyzed separately for both ITT and PP populations.

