5.4. Secondary Endpoints Analysis

5.4.1. Composite Endpoint of Four Clinical Events

Similar to the primary endpoint for this study, the composite clinical endpoint constructed as a win ratio hierarchy of the four components (see section 2.6) will be assessed using the F-S statistic with the following null and alternative hypotheses:

$$H_0: n'_{FW} \leq n'_{CW} \text{ versus } H_A: n'_{FW} > n'_{CW}$$

where n'_{FW} is the random variable of the number of winners for the FlowTriever System (i.e., counting the number of pairs in which the subject i in FlowTriever System does better than those in CDT arms) while n'_{CW} is the random variable of the number of winners for CDT (i.e., counting the number of pairs in which the subject i in FlowTriever System does worse than those in CDT arms). Additionally, the 95%CI of the win ratio of the treatment effect of this endpoint will be presented.

This composite endpoint will be assessed in both ITT and PP populations. If the results of the ITT and PP populations are similar, it indicates robust confidence on the treatment effect of FT relative to CDT.

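### The win-ratio bootstrap in SAP 5.3 draws a fixed 275 subjects per arm instead of the number analysed, so its 95% CI is too narrow when fewer are analysed, as is very likely in PP

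*SAP*

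**What the plan says.** SAP 5.3 introduces the FT and CDT groups as having n_F and n_C subjects. The numbered bootstrap steps then switch to capitals. In step 1 the FT draw is of size N_F, given in brackets as "275) with replacement from the original FT group and a random sample". The CDT draw is of size N_C, taken "with replacement from original CDT group. In this study", after which the SAP states S_F = S_C. Step 5 reads: "Obtain the 2.5%ile and 97.5%ile of the bootstrap distribution which are the estimated limits of the 95% confidence interval of the win ratio". No rescaling is mentioned.

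The same section says that "the estimation of the win ratio of the treatment effect of the primary endpoint will be assessed in both ITT and PP populations". On the sizes of those populations, SAP 3.1 says "This study will consist of up to 550 subjects with acute PE who meet the eligibility criteria" and removes randomised subjects who had no treatment or no data. SAP 3.2 says "Per Protocol (PP) population is a subset of ITT population that adhere to the protocol"; possible reasons for exclusion are non-compliance, deviations, withdrawal and receipt of another PE treatment.

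For the F-S test, SAP 5.2 builds the variance from n_FT and n_CDT, which "are the number of subjects in FlowTriever and CDT" arms. For the four-component hierarchy, SAP 5.4.1 adds: "Additionally, the 95%CI of the win ratio of the treatment effect of this endpoint will be presented". It names no method for that interval.

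**The concern.** A bootstrap interval takes its width from the size of the resample. If m subjects are drawn per arm from n observed, the bootstrap standard error behaves like 1/sqrt(m), while the true standard error behaves like 1/sqrt(n). With m fixed at 275 and n smaller, the interval claims precision that the data do not have.

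This is the only interval the SAP specifies for the primary effect estimate. PP would be given the resampling precision of 275 per arm however many subjects it had lost. SAP 5.3 reads similar ITT and PP results as a sign of robustness, yet the loss of information from ITT to PP would not show in the width of the interval. The F-S test uses the actual arm sizes, so the p-value and the interval would rest on different sample sizes and could disagree near the boundary.

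**Working it through.** **Where 275 comes from.** SAP 5.1 gives up to 550 randomised subjects and SAP 2.1 gives 1:1 allocation: 550/2 = 275. The required number in SAP 5.1 is 432, and 432/2 = 216 per arm. The ceiling therefore leaves room for 1 − 432/550 = 21.5% of subjects not to contribute. The 432 itself cannot be reproduced because the component event rates are not given, but this point does not depend on it.

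**Width factor.** Assume similar variance per subject in the two arms, on the log win-ratio scale. The bootstrap variance is then proportional to 2/275 and the true variance to 1/n_F + 1/n_C, so

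f = sqrt[(2/275) / (1/n_F + 1/n_C)], which is sqrt(n/275) for equal arms, and

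coverage ≈ 2Φ(1.96 f) − 1.

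Worked example at 216 per arm: f = sqrt(216/275) = 0.886; 1.96 × 0.886 = 1.737; coverage = 91.8%. The miss rate on the lower side is 4.1% instead of 2.5%.

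The SAP gives no expected PP size, so the arm sizes below are illustrative.

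| n_F / n_C | Width factor f | Coverage |
|---|---|---|
| 275 / 275 | 1.000 | 95.0% |
| 270 / 270 | 0.991 | 94.8% |
| 262 / 262 | 0.976 | 94.4% |
| 250 / 250 | 0.953 | 93.8% |
| 230 / 230 | 0.914 | 92.7% |
| 216 / 216 | 0.886 | 91.8% |
| 250 / 265 | 0.967 | 94.2% |
| 250 / 300 | 0.996 | 94.9% |

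**Direction.** Because 1/n_F + 1/n_C is at least 4/(n_F + n_C), and the total cannot exceed 550, the sum is at least 4/550 = 2/275. Under the equal-variance assumption f therefore cannot exceed 1. A slight reversal is possible if the variances differ: with 270/280 and variances 1 and 1.2, f² = (2.2/275) / (1/270 + 1.2/280) = 0.008000/0.007989, so f = 1.001.

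**Simulation of the five-level hierarchy.** There were 4,000 trials per row and 1,000 percentile-bootstrap draws, with independent components. All rates are assumptions:

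- FT: death 1%, ICH 0.3%, major bleeding 4%, deterioration or bailout 4%, ICU none / up to 24 h / over 24 h 45/30/25%.
- CDT: 2%, 0.8%, 7%, 7% and 30/35/35%.
- True win ratio: 1.72.

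| n_F / n_C | Coverage, drawing actual n | Coverage, drawing 275 | Mean width ratio |
|---|---|---|---|
| 262 / 262 | 94.8% | 94.2% | 0.977 |
| 250 / 250 | 94.9% | 93.8% | 0.954 |
| 230 / 230 | 95.2% | 92.6% | 0.915 |
| 216 / 216 | 95.1% | 91.2% | 0.885 |
| 250 / 265 | 94.7% | 94.0% | 0.966 |
| 250 / 300 | 95.2% | 95.0% | 0.993 |

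The Monte Carlo standard error of coverage is about 0.4 points.

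A separate run of 1,000 trials per row used different assumed rates. At 216 per arm, drawing 275 instead of 216 gave 91.5% against 94.6% with a true win ratio of 1.72, and 92.2% against 95.0% under the null. Mean log widths were 0.529 against 0.597, and 0.522 against 0.591. At 250 per arm that run was too small to separate the two draws under the null (93.6% against 93.1%), but the mean widths still differed as the formula predicts (0.523/0.548 = 0.954).

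**The case against.** The strongest reply is that the bracketed 275 only shows the value of N_F at full 1:1 enrolment. The draw size is written as a symbol, the CDT draw carries no number, and SAP 5.3 uses capitals elsewhere for counts in the dataset. The equality S_F = S_C cannot be literal, since samples from two different arms cannot be the same; it may mean only that equal arms were planned. The protocol's Statistical Methodology section mentions a bootstrap without fixing a draw size. A sensible programmer might resample the observed arms without comment.

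That reading is possible, but the SAP does not state it. Section 5.3 defines n_F and n_C and then does not use them in the algorithm. One number also cannot serve both ITT and PP unless the two coincide. Two analysts could follow the text differently and report different intervals.

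Other parts of the objection stand. The effect is close to nil for an ITT set near 550. The larger losses of coverage need roughly 16–21% of the ceiling to be missing, and the 216 row is the required sample size, not a forecast of PP. The hypothesis test does not use this interval, and the SAP sets no criterion based on its width. The reach to 5.4.1 is conditional, because that section does not cite the 5.3 steps.

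**Conclusion.** The concern holds. Followed as written, the bootstrap gives a win-ratio 95% CI that is too narrow whenever fewer than 550 subjects are analysed in roughly equal arms. For PP this is very likely, because PP is a subset of an ITT set that is itself capped at 550. The interval is about 1% too narrow at 270 per arm, 5% at 250 and 11% at 216, with coverage of 94.8%, 93.8% and 91.8%. These figures assume similar variance per subject in the two arms and illustrative arm sizes; they need no event rates. The primary test is untouched. The error reaches the interval around the primary effect estimate in ITT and PP, and the four-component interval if the same steps are used. It should be corrected before the analysis. Its practical weight depends on how many subjects PP excludes.

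**What to change.** In step 1 of SAP 5.3, delete the bracketed 275 and the statement S_F = S_C. State that each bootstrap sample draws n_F subjects from the FT arm and n_C from the CDT arm, where n_F and n_C are the numbers analysed in each arm of the population concerned (ITT or PP). Add to SAP 5.4.1 that the four-component interval uses the same steps.

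This costs one sentence, with no new data and no added programming. The intervals become slightly wider, most visibly in PP, and have the intended coverage. If 275 was only a placeholder, nothing else changes.

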5.4. Secondary Endpoints Analysis

5.4.1. Composite Endpoint of Four Clinical Events

Similar to the primary endpoint for this study, the composite clinical endpoint constructed as a win ratio hierarchy of the four components (see section 2.6) will be assessed using the F-S statistic with the following null and alternative hypotheses:

$$H_0: n'_{FW} \leq n'_{CW} \text{ versus } H_A: n'_{FW} > n'_{CW}$$

where n'_{FW} is the random variable of the number of winners for the FlowTriever System (i.e., counting the number of pairs in which the subject i in FlowTriever System does better than those in CDT arms) while n'_{CW} is the random variable of the number of winners for CDT (i.e., counting the number of pairs in which the subject i in FlowTriever System does worse than those in CDT arms). Additionally, the 95%CI of the win ratio of the treatment effect of this endpoint will be presented.

This composite endpoint will be assessed in both ITT and PP populations. If the results of the ITT and PP populations are similar, it indicates robust confidence on the treatment effect of FT relative to CDT.

5.4.2. All-cause Mortality at Discharge/at 7 Days after the Index Procedure

All-cause mortality, assessed at hospital discharge or at 7 days after the index procedure, whichever is sooner, will be analyzed as with the following null and alternative hypotheses:

PROPRIETARY AND CONFIDENTIAL

The information contained in this document is the sole property of Inari Medical

	PEERLESS Study: Statistical Analysis Plan	Version 5.0 March 22, 2024 Page 19 of 25
---	--	--

$H_0: p_{DF} \geq p_{DC}$ versus $H_A: p_{DF} < p_{DC}$

where p_{DF} represents the proportion of mortalities in the FlowTriever System group while p_{DC} represents the proportion of mortalities in the CDT group. The hypothesis will be tested using a Fisher's exact test.

5.4.3. All-cause Mortality within 30 Days from Index Procedure

All-cause mortality within 30 days will be analyzed as with the following null and alternative hypotheses:

$H_0: p_{D30F} \geq p_{D30C}$ versus $H_A: p_{D30F} < p_{D30C}$

where p_{D30F} represents the proportion of mortalities within 30 days in the FlowTriever System group while p_{D30C} represents the proportion of mortalities within 30 days in the CDT group. The hypothesis will be tested using a Fisher's exact test.

5.4.4. Intracranial Hemorrhage

Intracranial hemorrhage (ICH), assessed at hospital discharge or at 7 days after the index procedure, whichever is sooner, will be analyzed as with the following null and alternative hypotheses:

$H_0: p_{ICHF} \geq p_{ICHc}$ versus $H_A: p_{ICHF} < p_{ICHc}$

where p_{ICHF} represents the proportion of subjects with ICH in the FlowTriever System group while p_{ICHc} represents the proportion of subjects with ICH in the CDT group. The hypothesis will be tested using a Fisher's exact test.

5.4.5. Major Bleeding per ISTR³ Definition

Major bleeding, per ISTR³ definition, assessed at hospital discharge or at 7 days after the index procedure, whichever is sooner, will be analyzed as with the following null and alternative hypotheses:

$H_0: p_{BF} \geq p_{BC}$ versus $H_A: p_{BF} < p_{BC}$

where p_{BF} represents the proportion of subjects with major bleeding in the FlowTriever System group while p_{BC} represents the proportion of subjects with major bleeding in the CDT group. The hypothesis will be tested using a Fisher's exact test.

5.4.6. Clinical Deterioration and / or Escalation to a Bailout Therapy

Clinical deterioration defined by hemodynamic or respiratory worsening, and/or escalation to a bailout therapy, assessed at hospital discharge or at 7 days after the index procedure, whichever is sooner, will be analyzed as with the following null and alternative hypotheses:

PROPRIETARY AND CONFIDENTIAL

The information contained in this document is the sole property of Inari Medical

	PEERLESS Study: Statistical Analysis Plan	Version 5.0 March 22, 2024 Page 20 of 25
---	--	--

$H_0: p_{CF} \geq p_{CC}$ versus $H_A: p_{CF} < p_{CC}$

where p_{CF} represents the proportion of subjects with clinical deterioration / a bailout therapy in the FlowTriever System group while p_{CC} represents the proportion of subjects with clinical deterioration / a bailout therapy in the CDT group. The hypothesis will be tested using a Fisher's exact test.

5.4.7. ICU admission and ICU length of stay

ICU admission and ICU length of stay, post index procedure and following the index procedure, will be analyzed as with the following null and alternative hypotheses:

$H_0: p_{IF1} \leq p_{IC1}$ and $p_{IF2} \geq p_{IC2}$ and $p_{IF3} \geq p_{IC3}$ versus $H_A: p_{IF1} > p_{IC1}$ or $p_{IF2} < p_{IC2}$ or $p_{IF3} < p_{IC3}$

where p_{IF1} represents the proportion of subjects without ICU admission in the FlowTriever System group, p_{IF2} represents the proportion of subjects with 0-24 hours ICU stay in the FlowTriever System group, p_{IF3} represents the proportion of subjects with > 24 hours ICU stay in the FlowTriever System group, p_{IC1} represents the proportion of subjects without ICU admission in the CDT group, p_{IC2} represents the proportion of subjects with 0-24 hours ICU stay in the CDT group, p_{IC3} represents the proportion of subjects with > 24 hours ICU stay in the CDT group. The hypothesis will be tested using a Fisher's exact test.

